5 GENERAL METHODOLOGY AND CONVENTIONS

Unless otherwise specified, all statistical analysis will be performed by Cohort and separately by trial parts. For subjects in Part B and Part C of the trial, summaries will also be presented by age-group 18-55 years and 56-85 years. The primary immunogenicity analysis for each Part B and Part C Cohort will be performed after completion of 1 month or 3 weeks post-dose visit. All other data may be analyzed periodically.

For data analysis of local reactions and systemic events, reactogenicity events (i.e., local reactions and systemic events) within 7 days of trial IMP injection will be included in the tables, figures and listings.

5.1 Hypotheses and decision rules

Statistical hypotheses will only be tested in Part B, separately for each cohort.

Immunobridging success in each Part B Cohort requires demonstration of non-inferior antibody levels in both geometric mean titers (GMTs) and SR rates against the B.1.1.7 and B.1.617.2 variants of concern (VOC) in both Cohorts 1 and 6; and against B.1.617.2 in Cohort 4 after the booster dose vs antibody levels against the reference strain, observed in subjects from the Phase III BNT162-02/C4591001 trial, after two doses of BNT162b2. In addition, non-inferiority of immune response against reference strain 21 days after one dose of BNT162b2 (B.1.1.7 + B.1.617.2) in Cohort 6 subjects with prior evidence of infection vs immune response against reference strain 1 month after two doses of BNT162b2 in subjects without evidence of infection will also be assessed using the same success criteria.

5.1.1 GMT non-inferiority – Part B

The statistical hypothesis for GMT non-inferiority of each variant and reference strain is:

$$H_0: \mu_{\text{ratio}} \leq 0.67 \text{ vs } H_1: \mu_{\text{ratio}} > 0.67$$

where 0.67 corresponds to a 1.5-fold margin for non-inferiority, and μ_{ratio} is the ratio of GMT of VOC specific NT at 1 month after booster dose of BNT162b2 (B.1.1.7 + B.1.617.2) for Cohort 1 and BNT162b2 (B.1.617.2) for Cohort 4 to the reference NT at 1 month after second dose of BNT162b2 or ratio of GMT of reference strain NT at 3 weeks after one dose of BNT162b2 (B.1.1.7 + B.1.617.2) to 1 month after the second dose of BNT162b2 (defined as the geometric mean ratio [GMR]).

GMT VOC non-inferiority success for Cohort 1 will be declared if the lower bound of the 2-sided 95% confidence intervals (CIs) for (1) $GMR_{B.1.1.7/ref}$ (GMT of B.1.1.7 ÷ GMT of

reference) and (2) $GMR_{B.1.617.2/ref}$ (GMT of B.1.617.2 ÷ GMT of reference) are both greater than 0.67. GMT reference strain non-inferiority success for Cohort 6 will be declared if the lower bound of the 2-sided 95% CI for $GMR_{ref/ref}$ (GMT of reference ÷ GMT of reference) is greater than 0.67. GMT VOC non-inferiority success for Cohort 4 will be declared if the lower bound of the 2-sided 95% confidence interval $GMR_{B.1.617.2/ref}$ (GMT of B.1.617.2 ÷ GMT of reference) is greater than 0.67.

5.1.2 SR non-inferiority – Part B

The statistical hypothesis for SR non-inferiority for each variant and reference strain is:

$$H_0: \pi_{\text{variant}} - \pi_{\text{reference}} \leq -10\% \text{ vs}$$

$$H_1: \pi_{\text{variant}} - \pi_{\text{reference}} > -10\%$$

where π_{variant} is the SR against the VOC at 1 month after booster dose of BNT162b2 (B.1.1.7 + B.1.617.2) for Cohort 1 and BNT162b2 (B.1.617.2) for Cohort 4 or SR against the reference strain at 3 weeks after one dose of BNT162b2 (B.1.1.7 + B.1.617.2) and $\pi_{\text{reference}}$ is the SR against the reference strain at 1 month after second dose of BNT162b2.

The SR VOC non-inferiority success for Cohort 1 will be declared if the lower bounds of the 2-sided 95% CIs for the difference of:

1. SR of B.1.1.7 – SR of reference and
2. SR of B.1.617.2 – SR of reference

are both greater than -10%. The SR reference strain non-inferiority success for Cohort 6 will be declared if the lower bounds of the 2-sided 95% CIs for the difference in SRs of reference is greater than -10%. The SR VOC non-inferiority success for Cohort 4 will be declared if the lower bound of the 2-sided 95% CI for the difference of SR of B.1.617.2 – SR of reference is greater than -10%.

5.1.3 Sample size

Planned enrollment is ~1,470 subjects; ~120 in Part A (~20 in each of the six Cohorts), ~1,125 in Part B (~375 in each of the three Cohorts), and ~225 in Part C (~80 in each of Cohort 7 and Cohort 8 and ~45 in Cohort 9).

5.1.3.1 Part A

The sample size for Part A of the trial is not based on any statistical hypothesis testing. Part A comprises 20 subjects per Cohort, corresponding to a total of 120 subjects.

5.1.3.2 Part B

Geometric mean ratio

Assuming an observed GMR of 0.8 and standard deviation of 0.7 (log scale), 300 evaluable subjects will provide 87% power at $\alpha = 0.025$ (1-sided) to demonstrate non-inferiority of VOC vs reference strain response. The table below demonstrates the power for testing GMT for each variant strain vs reference strain at $\alpha = 0.025$ (1-sided):

Test	Margin	Assumed GMR	Number of evaluable subjects	SD log scale	Power
VOC vs reference strain GMT non-inferiority	0.67	0.8	300	0.65	92%
				0.70	87%
				0.75	82%
Reference strain vs reference strain GMT non-inferiority	0.67	0.8	240	1.05	46%
		0.9	240	1.05	87%
		1.0	240	1.05	99%

Abbreviations: GMT = geometric mean titer; GMR = geometric mean ratio; SD = standard deviation; VOC = variant of concern.

Seroresponse

Assuming an SR difference of -3% (variant SR – reference SR) and 97% reference SR, 300 evaluable subjects will provide 96% power at alpha = 0.025 (1-sided). The table below demonstrates the power for testing SR for each variant strain vs reference strain at alpha = 0.025 (1-sided) to demonstrate non-inferiority of VOC vs reference strain response.

Test	Margin	SR difference	Number of evaluable subjects	Reference SR	Power
VOC vs reference strain SR non-inferiority	-10%	-3%	300	98%	98%
				97%	96%
				95%	90%
Reference strain vs reference strain SR non-inferiority	-10%	-3%	240	98%	95%
				97%	91%
				95%	83%
	-10%	-5%	240	98%	65%
				97%	59%
				95%	50%

Margin is the lower bound of 95% CI.

Abbreviations: CI = confidence interval; SR = seroresponse; VOC = variant of concern.

Therefore, to account for a 20% non-evaluable rate, approximately 375 subjects will be enrolled for each cohort.

In Cohort 6, assuming 80% subjects with evidence of prior infection, 240 evaluable subjects will contribute to the hypotheses for non-inferiority of immune response against reference strain. Tables above also present the power to demonstrate non-inferiority of immune response against reference strain under various assumptions in terms of GMT and SR.

5.1.3.3 Part C

No confirmatory hypothesis testing is planned for Part C. However, exploratory analysis may be performed on selected endpoints. To describe the immune profile, 80 evaluable subjects per Cohort in Cohorts 7 and 8 and 40 evaluable subjects in Cohort 9 are

considered adequate based on experience in previous trials conducted by BioNTech in the BNT162 program.

Geometric mean ratio

The table below demonstrates the power for testing GMT for variant strain post BNT162b2 vs post BNT162b2 (B.1.1.529) at alpha = 0.025 (1-sided) to demonstrate superiority.

Test	Margin	Assumed GMR (GMT variant + GMT ref)	Number of evaluable subjects	Standard deviation (log value)	Power
GMT superiority	1.0	1.75	80	1.0	94%

Margin is the lower bound of 95% CI for GMR.

Abbreviations: GMT = geometric mean titer; GMR = geometric mean ratio.

To account for ~11% non-evaluable rate, Part C will randomize 225 subjects in a 2:2:1 ratio (90 each for Cohorts 7 and 8 and 45 in Cohort 9).

5.1.4 Multiplicity considerations

5.1.4.1 Part A

For Part A, there is no hypothesis testing.

5.1.4.2 Part B

The objectives for Cohort 1, 4, and 6 will be evaluated independently. Subjects in each cohort are different populations. Therefore, no type I error adjustments will be applied to the assessments across the three cohorts. A fixed sequential testing procedure will be used for multiplicity control for each cohort separately across Part B, all at 1-sided 2.5% level of significance.

For Cohort 1 and Cohort 4, the hypotheses will be tested in the following sequence:

1. Non-inferiority in terms of GMTs
2. Non-inferiority in terms of SRs

For Cohort 6, the hypotheses will be tested in the following sequence:

1. Non-inferiority of immune response against reference strain in terms of GMT
2. Non-inferiority of immune response against reference strain in terms of SR
3. Non-inferiority of immune response against VOCs vs reference strain in terms of GMTs
4. Non-inferiority of immune response against VOCs vs reference strain in terms of SRs

5.1.4.3 Part C

No confirmatory hypothesis testing is planned for Part C.

5.2 General methods

All statistical procedures will be completed using SAS version 9.4 or higher. Unless otherwise specified, 2-sided 95% CIs for all endpoints in the statistical analysis, will be presented. Data assessed after the vaccination with a non-trial COVID-19 vaccine will be excluded from all immunogenicity analyses.

Analysis of antibody titers will be performed on natural log scale and the results will be exponentiated back to original scale.

For each subject and each time point two titers for each variant will be determined, as each sample will be measured in replicate. The response per subject, variant, and time point is defined as the geometric mean of the two titers.

All relevant subject data, including those derived will be presented in individual subject data listings.

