
To compare the immune response against VOCs 3 weeks after one dose of multivalent vaccine BNT162b2 (B.1.1.7 + B.1.617.2) in COVID-19 vaccine-naïve subjects with evidence of prior infection to the immune response 1 month after two doses of multivalent vaccine BNT162b2 (B.1.1.7 + B.1.617.2) in COVID-19 vaccine-naïve subjects without evidence of infection.
	
BNT162b2 (B.1.1.7 + B.1.617.2) in subjects without evidence of infection.
 
 
• GMTs and SRs of VOCs NT 3 weeks after one dose of BNT162b2 (B.1.1.7 + B.1.617.2) in subjects with evidence of prior infection and 1 month after two doses of BNT162b2 (B.1.1.7 + B.1.617.2) in subjects without evidence of infection.
 
• GMR of VOCs NT 3 weeks after one dose of BNT162b2 (B.1.1.7 + B.1.617.2) in subjects with evidence of prior infection to the VOCs NT 1 month after two doses of BNT162b2 (B.1.1.7 + B.1.617.2) in subjects without evidence of infection.
 
• The difference in SRs to VOCs NT 3 weeks after one dose of BNT162b2 (B.1.1.7 + B.1.617.2) in subjects with evidence of prior infection and to the VOCs NT 1 month after two doses of BNT162b2 (B.1.1.7 + B.1.617.2) in subjects without evidence of infection.
 
	
 
• VOC specific NTs (B.1.1.7, B.1.617.2, B.1.1.529.5 [Omicron BA.5])
 

Exploratory objectives		

To evaluate SARS-CoV-2 viral sequences in subjects.
	
 
• SARS-CoV-2 S antigen sequences or whole viral genome sequencing of interest.
 
	
 
• Viral sequences
 

To evaluate the immune response over time to prophylactic multivalent vaccine BNT162b2 (B.1.1.7 + B.1.617.2) or monovalent vaccine BNT162b2 (B.1.617.2), and persistence of immune response in subjects with and without prior COVID-19 vaccination.
	
 
• GMC/GMT and GMFR at baseline and 1, 6, and 12 months after completion of vaccination.
 
• SRs for reference strain and B.1.1.7 and B.1.617.2 variant strains.
 
	
 
• Reference and VOC specific NTs
 
• RBD and full length S-binding or S1-binding Ig levels
 

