	infection and to the VOCs NT 1 month after two doses of BNT162b2 (B.1.1.7 + B.1.617.2) in subjects without evidence of prior infection.	
Exploratory objectives		
To evaluate SARS-CoV-2 viral sequences in subjects.	
 SARS-CoV-2 S antigen sequences or whole viral genome sequencing of interest. 	
 Viral sequences
To evaluate the immune response over time to prophylactic multivalent vaccine BNT162b2 (B.1.1.7 + B.1.617.2) or monovalent vaccine BNT162b2 (B.1.617.2), and persistence of immune response in subjects with and without prior COVID-19 vaccination.	
 GMC/GMT and GMFR at baseline and 1, 6, and 12 months after completion of vaccination. SRs for reference strain and B.1.1.7 and B.1.617.2 variant strains. 	
 Reference and VOC specific NTs RBD and full-length S-binding or S1-binding Ig levels
To evaluate cross-neutralization of vaccine-induced antibodies to emerging SARS-CoV-2 variants.	
 For a subset of subjects, after any dose of multivalent vaccine, BNT162b2 (B.1.1.7 + B.1.617.2) or monovalent vaccines BNT162b2 and BNT162b2 (B.1.617.2) vaccines, measured cross-neutralization of other SARS-CoV-2 variants (e.g., using VNT or pVNT). 	
 NT data
To describe B-cell responses after one or two and three doses of the multivalent vaccine BNT162b2 (B.1.1.7 + B.1.617.2).	
For a subset of Cohort 6 subjects in Part B:
 
 Characterization of SARS-CoV-2 S protein-specific B cells to identify B cells recognizing conserved and strain-specific epitopes. 	
 Frequency and phenotypic characterization of SARS-CoV-2 spike-specific B cells
To describe the T cell-mediated immune response after one or two and three doses of the multivalent vaccine BNT162b2 (B.1.1.7 + B.1.617.2).	
For a subset of Cohort 6 subjects in Part B:
 
 CMI responses including CD4 and CD8 T-cell responses to S and RBD antigens of the reference strain and the B.1.1.7 and B.1.617.2 variant strains. 	
 Reference and VOC specific CD4 and CD8 T-cell responses (e.g., using ELISpot, ICS)

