To describe the humoral immune response against SARS-CoV-2 variants after one dose of BNT162b2 (B.1.1.529) or after one dose of BNT162b2 or a post SARS-CoV-2 infection in RNA-based COVID-19 vaccine-experienced subjects with history of SARS-CoV-2 infection.	
 • GMT of VOC NT at baseline and 7 days, 1 month, and 3 months after the trial start for Cohorts 7, 8, and 9, and 6 and 12 months after the trial start for Cohorts 7 and 8. 	
 • VOC specific NTs
Exploratory objectives		
To evaluate SARS-CoV-2 viral sequences in subjects.	
 • SARS-CoV-2 S antigen sequences or whole viral genome sequencing of interest. 	
 • Viral sequences
To evaluate cross-neutralization of vaccine-induced antibodies to ancestral and emerging SARS-CoV-2 variants.	
 • For a subset of subjects, after one dose of monovalent vaccine BNT162b2 (B.1.1.529) or BNT162b2, measured cross-neutralization of other SARS-CoV-2 variants (e.g., using VNT or pVNT). 	
 • NT data
To evaluate the immune response over time to prophylactic monovalent vaccine BNT162b2 (B.1.1.529) or BNT162b2 and persistence of immune response in RNA-based COVID-19 vaccine-experienced subjects with history of SARS-CoV-2 infection.	
 • GMC/GMT and GMFR at baseline, 7 days, and 1, 3, 6, and 12 months after completion of vaccination. • Seroreponse for B.1.1.529 variant strain. 	
 • Reference and VOC specific NTs • RBD and full length S-binding or S1-binding Ig levels
To evaluate the immune response to SARS-CoV-2 in subjects.	
 • GMC/GMT and GMFR at baseline, 7 days, and 1, 3, 6, and 12 months after completion of vaccination. 	
 • Nucleocapsid (N)-binding Ig levels
To describe the incidence of confirmed COVID-19 at 1 year follow-up period in subjects who received one dose of monovalent BNT162b2 (B.1.1.529) or BNT162b2.	
 • Incidence of confirmed COVID-19 cases per 1,000 person-years of follow-up. 	
 • Number of confirmed COVID-19 cases

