An important protocol deviation is a protocol deviation that, in the opinion of the sponsor’s clinician, would materially affect assessment of immunogenicity, e.g., subject receipt of a prohibited vaccine or medication that might affect immune response or a medication error with suspected decrease in potency of the vaccine.

- a) The sampling windows with grace period specified in Table 7 will be used to define the valid samples for Immunogenicity Analysis Set.
 - b) The sampling windows per protocol specified in Table 7 will be used to define the valid samples for Immunogenicity Analysis Per Protocol Set.
 - c) In cohort 9 all randomized subjects who have a valid and determinate immunogenicity result from the blood sample and have no other important protocol deviations that can confound immunogenicity data, will be included in the Immunogenicity Analysis Set.
 - d) Participants with missing baseline data will be included in this population, providing other criteria are met
- Abbreviation: IMP = investigational medicinal product.

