6.2.3 Immunogenicity endpoints – Part C

6.2.3.1 GMT of VOC specific NT at baseline and at each post-vaccination time point for Cohorts 7, 8 and 9

The same analysis as described in [Section 6.2.1.1](#) will be repeated for Part C Cohorts 7, 8 and 9.

A bar chart including LLOQ and ULOQ lines and with different color codes for data from subjects according to their N-binding assessment for the respective visit, time point and line plot of GMTs and the associated 2-sided 95% CIs will be presented at each post-vaccination time point for each cohort by trial part.

The analysis will be performed on Immunogenicity Analysis Per Protocol Set as well. The number of subjects with valid and determinate assay results for the specified assay at each post-vaccination time point and a summary of GMT and its associated 2-sided 95% CIs will be presented by cohort.

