6.3.2 Exploratory – Part B

6.3.2.1 GMT, GMFR and SR of Reference and VOC specific NT at each post vaccination time point for Cohort 1 and 4 in BNT162b2-experienced subjects

The same analysis as described in [Section 6.2.1.1](#) will be repeated for GMT and GMFR at each post-vaccination time point.

The same analysis as described in [Section 6.2.1.2](#) will be repeated for SR at each post-vaccination time point.

6.3.2.2 GMT, GMFR and SRs of Reference and VOC specific NT at each post vaccination time point for Cohort 6 in COVID-19 vaccine-naïve subjects

The same analysis as described in [Section 6.2.1.1](#) will be repeated for GMT and GMFR at each post-vaccination time point.

The same analysis as described in [Section 6.2.1.2](#) will be repeated for SR at each post-vaccination time point.

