8.2 Changes in interim analysis

the safety and immunogenicity analysis with data up to 1 month post dose for Part A (Cohort 1, 3, 4 and 5), 1 month post Dose 2 for Part A (Cohort 2 and 6) will be performed. The primary immunogenicity analysis for all Part B cohorts and for Part C Cohorts 7 and 8 will be performed in the final analysis for clinical study report.

8.3 Withdrawal of primary objectives to demonstrate the non-inferiority of immune response against VOC (B.1.1.7 and B.1.617.2) after two doses of multivalent vaccine BNT162b2 (B.1.1.7 + B.1.617.2) in terms of GMT and SR for COVID-19 vaccine-naïve subjects in Part B Cohort 6

In COVID-19 vaccine naïve individuals (recruited into cohort B6), the original primary immunogenicity objectives were to demonstrate the non-inferiority of immune response against Variants of Concern (B.1.1.7 and B.1.617.2) after two doses of multivalent vaccine BNT162b2 (B.1.1.7 + B.1.617.2) to the immune response after two doses of original BNT162b2 in subjects without evidence of infection from the Phase I/ II/ III trial BNT162-02/ C4591001 in terms of geometric mean titer (GMT) and seroresponse rate (SR).

By the time the cohort had been fully recruited in August 2022, approximately 75% participants recruited into cohort B6 – required to be without known history of SARS-CoV-2 infection, self-reported at the screening visit according to the exclusion criteria - retrospectively turned out to be seropositive for SARS-CoV-2 by planned N-binding antibody assessment at baseline. The cohort hence was COVID-19 vaccine-naive, but not SARS-CoV-2-naïve as originally foreseen.

In BNT162-17 protocol version v7.0, new primary and secondary immunogenicity objectives for COVID-19 vaccine-naïve subjects in Part B were introduced aiming to support FDA authorization of a single-dose primary regimen of the 2023/2024 season variant-adapted BNT162b2 vaccine targeting XBB.1.5 in previously unvaccinated individuals with and without previous SARS-CoV-2 infections. The new primary immunogenicity objectives were thus to demonstrate the non-inferiority of immune response against reference strain after one dose of multivalent vaccine BNT162b2 (B.1.1.7 + B.1.617.2) in COVID-19 vaccine-naïve subjects with evidence of prior infection (cohort B6 of BNT162-17) to the immune response after two doses of original BNT162b2 in subjects without evidence of infection from the Phase I/ II/ III trial BNT162-02/ C4591001 in terms of GMT and SR.

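### The late GMT, GMFR and SR tables (6 and 12 months; also 3 months in Part C) keep samples taken after a new SARS-CoV-2 infection, so read as vaccine persistence they are biased upward by an unknown factor

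*SAP*

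**What the plan says.** SAP 5.2 names one event that removes later titers: "Data assessed after the vaccination with a non-trial COVID-19 vaccine will be excluded from all immunogenicity analyses". The analysis sets in SAP Section 4 add no rule for infection. The examples given there of an important protocol deviation are "subject receipt of a prohibited vaccine or medication that might affect immune response or a medication error with suspected decrease in potency of the vaccine". The Immunogenicity Analysis Set and its Per Protocol counterpart differ only in the sampling window.

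The late time points serve a persistence aim. The Part B exploratory objective in Protocol Section 3 concerns "persistence of immune response in subjects with and without prior COVID-19 vaccination", with the estimand "GMC/GMT and GMFR at baseline and 1, 6, and 12 months after completion of vaccination" (SAP 2.1, Table 3). In Part C the secondary estimand is "GMT of VOC NT at baseline and 7 days, 1 month, and 3 months after the trial start for Cohorts 7, 8, and 9", extended to 6 and 12 months for Cohorts 7 and 8, and a separate exploratory objective names persistence.

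The analyses themselves carry no infection condition. For Part B, SAP 6.3.2 says that the Part A analysis "will be repeated for GMT and GMFR at each post-vaccination time point". For Part C, SAP 6.2.3.1 covers "GMT of VOC specific NT at baseline and at each post-vaccination time point for Cohorts 7, 8 and 9". Part A (6.2.1.1, 6.2.1.2) and the Part C exploratory tables (6.3.3.1) are written the same way.

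**The concern.** A trial subject can meet spike antigen again during follow-up in two ways: a further vaccine or an infection. The SAP removes samples after the first and keeps samples after the second. If infection raises titers, a 6- or 12-month GMT computed on everyone mixes what is left of the vaccine response with the boost from infection. It then shows less waning than vaccine recipients who stayed free of infection would show. SR is exposed too, because an infection can create a new rise of at least 4-fold over baseline in someone whose vaccine response had faded.

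At stake is how the durability tables are read. The SAP already treats infection as worth separating at the early Part B time points, when little time has passed for infections to occur. It has no such separation at 6 and 12 months, when more have had time to accumulate.

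**Working it through.** The documents give no sample size, power or infection rate for the late tables, so there is no planned figure to reproduce. The check has two parts.

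**1. Is there an infection rule anywhere for the late tables?**

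- SAP 3.4.1 defines absence of infection after vaccination for Part B and for the control trial only. The definition ends at the 1-month sample (after Dose 2 for Cohort 6, after the trial vaccination for Cohorts 1 and 4).
- SAP 6.1.2.1 to 6.1.2.4 offer infection-free sensitivity analyses for Cohorts 1 and 4 at 1 month, as optional analyses.
- SAP 6.1.2.5, 6.1.2.6 and 6.2.2.7 to 6.2.2.10, with Appendix 2, use comparators without evidence of infection, again for results at 3 weeks or 1 month.
- SAP 6.2.1.1, 6.2.1.2, 6.2.3.1, 6.3.2.1, 6.3.2.2 and 6.3.3.1 hold the late results and contain no infection rule.
- SAP 6.4 lists subgroups by age, obesity and diabetes, not by infection. SAP 5.3 uses observed data.
- The only link between infection and titers at late visits is the colour-coding of charts by N-binding status (6.2.1.1, 6.2.3.1). Confirmed COVID-19 (Parts B and C) and N-seroconversion (Part B) are reported separately as incidence.

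So no GMT, GMFR or SR beyond 1 month is planned without post-infection samples.

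**2. How large is the effect?**

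Let m be the mean log titer that would be seen without infection. Let q be the share of samples that follow a new infection and f the fold increase it causes. The pooled mean log titer is (1 − q)·m + q·(m + ln f) = m + q·ln f. Exponentiating gives

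reported GMT = infection-free GMT × f^q.

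GMFR carries the same factor, because baseline is taken before the first dose. Both q and f are assumptions:

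| f | q = 5% | 10% | 20% | 30% | 50% |
|---|---|---|---|---|---|
| 2 | 1.04 | 1.07 | 1.15 | 1.23 | 1.41 |
| 4 | 1.07 | 1.15 | 1.32 | 1.52 | 2.00 |
| 8 | 1.11 | 1.23 | 1.52 | 1.87 | 2.83 |

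Example: with q = 20% and f = 4, a true 4-fold decline would be reported as 4 / 1.32 = 3.03-fold.

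**3. What would censoring cost in precision?**

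The 95% confidence limits of a GMT are the GMT divided and multiplied by exp(1.96 × SD / √n). The SDs are borrowed from the power calculations, as an illustration. If 20% of samples are removed:

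- Part B, SD 0.7: n from 300 to 240, factor from 1.082 to 1.093.
- Part C, SD 1.0: n from 80 to 64, factor from 1.245 to 1.278.

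**The case against.** The strongest reply is that titers regardless of infection are a legitimate thing to describe, and that Section 5.2 does not show that the sponsor wanted anything else. It gives no reason for excluding samples after a non-trial vaccine. The protocol discontinues such subjects and takes no immunogenicity blood at their early termination visit (schedule of activities footnotes; Section 7.2), so the SAP sentence may simply follow trial conduct. Infected subjects stay in the trial and are sampled. This stands: a reader might infer from 5.2 that an infection-free estimand was intended, and the documents do not support that. What remains is that the estimand tables do not state the choice, while the objective speaks of persistence of the response to the vaccine.

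Second, persistence is named only in exploratory objectives. The secondary objectives of Parts A and C are to describe the immune response, and nothing affected is tested. That limits the weight of the point but does not remove it.

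Third, there is some mitigation: colour-coded charts, incidence tables and subject listings. None of these recalculates a titer summary. The colour-coding is also weakest where prior infection is common. All Part C subjects had a prior infection, and about 75% of Cohort 6 "retrospectively turned out to be seropositive for SARS-CoV-2 by planned N-binding antibody assessment at baseline" (SAP 8.3), so N-positivity there does not mark a new infection.

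Fourth, censoring has its own faults. If subjects with low titers are infected more often, removing them leaves a higher-titer remainder, which can also flatter durability. Between widely spaced visits, asymptomatic reinfections in subjects already N-positive will often be missed. Both points stand, and they are why censored tables should not replace the all-subject ones or be the sole basis for persistence statements.

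Finally, values above the upper limit of quantitation are set to that limit (SAP 3.1.2), which can compress the effect.

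**Conclusion.** The point holds for the descriptive GMT, GMFR and SR at 6 and 12 months in Parts A, B and C, and at 3 months in Part C. Relative to persistence without infection, GMT and GMFR are biased upward whenever some samples follow an infection (q > 0) that raises titers (f > 1). Over the assumed grid the factor runs from 1.04 to 2.83. The documents give no follow-up infection rate and no boost size, so only the direction is supported. SR moves the same way by an amount that cannot be derived.

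Three stronger readings are tempting and not supported:

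- The 75% seropositivity in Cohort 6 is not a follow-up infection rate. It was measured at baseline and built up before dosing over an unknown period. It cannot supply q.
- Late comparisons between cohorts are not shown to be distorted, because none is planned. The late summaries are per cohort; the planned ratios and SR differences are at 3 weeks or 1 month.
- The primary tests are not affected by this gap, because they do not use the late samples.

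The affected results are secondary (Parts A and C) or exploratory (Parts B and C). For Cohort 9, which receives no trial vaccine before its last visit at 3 months, the issue is further infection after Visit 1, not loss of a vaccine response. This is a worthwhile, inexpensive improvement to how persistence is reported.

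**What to change.** In SAP 6.2.1.1, 6.2.1.2, 6.2.3.1, 6.3.2.1, 6.3.2.2 and 6.3.3.1, add supplementary GMT, GMFR and SR tables that censor samples from the first evidence of new infection after Dose 1 (after Visit 1 for Cohort 9). Evidence would be any of:

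- a positive NAAT;
- confirmed COVID-19 or a COVID-19 adverse event;
- N-seroconversion, if baseline N-binding was negative;
- a pre-defined rise in N-antibody, if baseline N-binding was positive and quantitative levels exist.

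Extend the definition in SAP 3.4.1 to each late time point and to Parts A and C. Report the number of samples censored at each visit, by cohort. Keep the all-subject tables, say that they show titers regardless of infection, and interpret persistence from both sets.

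The cost is SAP wording and extra tables. NAAT, N-binding and adverse event data are already collected at follow-up visits, so no new sampling is needed. The trial ended on 04 October 2023, but SAP 8.3 shows the sponsor recording a later change in the SAP and study report, and the same route is open here.

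The downsides should be stated with the tables: smaller numbers at late visits (in Part A, losing 20% of 20 leaves 16 per cohort), possible selection of higher-titer subjects, and undetected asymptomatic reinfections, mainly in Part B Cohort 6 and Part C.
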